4.2 Inclusion Criteria

Patients will be eligible to enroll in the study if they meet **all** the following criteria:

1. Completed study TIRCON2012V1
2. Sexually active females of childbearing potential, including those who are perimenopausal (defined as less than 2 years since last menstrual period) must have a negative pregnancy test result at Visit 1 (if applicable; in cases where the investigator determines there is no reasonable risk of pregnancy because of significant incapacity, pregnancy testing will not be performed). In addition, if applicable, they must meet at least one of the following criteria:
 - Use an effective method of contraception during the study and within 30 days following their last dose of study medication, OR
 - Participate in a non-heterosexual lifestyle, OR
 - Have a male sexual partner who has been sterilized (supporting evidence required)

Approved methods of contraception will consist of the following or must follow local requirements:

- Oral contraceptive used in conjunction with condom, diaphragm, or spermicide
- Hormonal implant used in conjunction with condom, diaphragm, or spermicide
- Injectable contraceptive used in conjunction with condom, diaphragm, or spermicide
- Diaphragm or condom used with spermicide

If a hormonal contraception is used, it should have a Pearl index <1%.

Female patients who meet any of the following criteria are not of childbearing potential and therefore do not need to practice contraception:

- Post-menopausal (last menstrual period > 2 years ago)
 - Had a tubal ligation (supporting evidence required)
 - Had a hysterectomy or oophorectomy (supporting evidence required)
3. Fertile heterosexual males and/or their partners must agree to use an effective method of contraception during the study and for 30 days following the last dose of study medication
 4. Patients and/or their authorized legal representatives must provide signed and dated written informed consent prior to the first study intervention, and patients must be able to adhere to study restrictions, appointments, and evaluation schedules. Patients who are minors must sign an assent form as per local regulatory requirements.

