4.3 Exclusion Criteria

1. Withdrew from the study TIRCON2012V1 for reasons of safety
2. Plan to participate in another clinical trial at any time from the day of enrolment until 30 days post-treatment in the current study
3. Presence of any medical, psychological, or psychiatric condition which in the opinion of the investigator would cause participation in the study to be unwise.
4. Pregnant, breastfeeding, or planning to become pregnant during the study period.

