4.5 Patient Withdrawal

Patients have the right to withdraw from the study at any time and for any reason without consequence to future care by the investigator or study center.

A patient may be withdrawn from the study at any time, at the discretion of the investigator, for any of the following reasons:

- Medical or safety reasons considered significant by the patient and/or the investigator
- Requirement for concomitant medication that might interfere with the evaluation of study treatment or may be contraindicated
- Occurrence of other illnesses that might affect the patient's further participation in the study or evaluation of study treatment
- A protocol deviation that might interfere with study assessments, as judged by the investigator
- Repetitive patient non-compliance with the protocol or with instructions of the investigator
- Participation in another clinical trial at any time during the conduct of this study
- Any other situation where, in the opinion of the investigator, continuation of the study would not be in the best interest of the patient

A patient **must** be withdrawn from the study if any of the following conditions apply:

- Pregnant or planning to become pregnant (see [Section 7.2.4](#), Procedures in Case of Pregnancy)

- Occurrence of any adverse event characterized as life-threatening or disabling that is not associated with the patient's primary diagnosis and that is assessed as at least possibly related to study drug by the investigator or the sponsor
- Non-compliance with weekly hematology blood counts (3 or more consecutively missed visits will result in automatic withdrawal)
- Termination of the study by the sponsor
- Occurrence of moderate neutropenia or severe neutropenia/agranulocytosis (see [Section 7.2.1.8](#), Adverse Events of Special Interest)

Patients who decide to withdraw participation in the study should always be contacted, if possible, in order to ask about the reason for withdrawal, whether any adverse events (AEs) occurred, and use of concomitant medications. A withdrawn patient should return for an Early Termination Visit. All investigational product and materials should be returned. If any AEs occurred, the investigator must attempt to follow up the outcome for 30 days post-termination.

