4.5.2 Replacement of Patients Who Withdraw

Not applicable. The only individuals eligible for enrolment are those who completed treatment in study TIRCON2012V1.

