9.4.1.4 Analysis of Safety

All safety data reported and collected during deferiprone therapy for all patients will be presented in listings and summary tables to give an overview of the safety findings. For patients continuing on deferiprone in the extension study, this time period will be from the start of TIRCON2012V1 to the completion of TIRCON2012V1-EXT; for those who received placebo in the initial study and are switching to deferiprone in the extension study, it will be from the start to the completion of the extension study.

Adverse Events:

A summary table of adverse events will include the following information:

- Number of patients exposed to study treatment
- Number of patients experiencing at least one AE
- Number of patients experiencing at least one severe AE
- Number of patients experiencing at least one serious AE
- Number of patients experiencing at least one drug-related AE
- Number of deaths
- Total number of patients withdrawn
- Number of withdrawals due to AEs

All adverse experiences will be coded using MedDRA (Medical Dictionary for Regulatory Activities) and will be summarized by MedDRA System Organ Class (SOC) and Preferred Term. Adverse events will be defined as: 1) AEs that occurred or worsened (increased in intensity and/or frequency) on or after the first dose of study medication, 2) AEs with a

missing start date and a stop date on or after the first dose of study medication, 3) AEs with both a missing start and stop date. Events that occur within 14 days after treatment discontinuation will also be considered AEs. Serious adverse events that occur within 30 days after treatment discontinuation will be included in the database.

Adverse events will be summarized using the total number of AEs, the total number and percent of patients who experience an AE, and the number and percent of patients who experienced an AE within each SOC (and preferred term within an SOC). AEs will also be presented by intensity (mild, moderate, severe), by seriousness (serious, non-serious), and by relationship to study medication (at least possibly related, not related). The number and percentage of patients who are withdrawn from the study due to AEs will be calculated, and the AEs involved will be summarized in a frequency table. Time to onset and duration of all AEs with an incidence of >5%, and of any AEs of special interest (e.g., worsening of dystonia), will be summarized with descriptive statistics.

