3.3 Analysis Populations

The following study populations will be used for analysis: Safety, Intent-to-Treat (ITT), and Per-Protocol (PP). The safety population will be used for the analysis of safety endpoints. The ITT population will represent the primary analysis population for the evaluation of efficacy endpoints, and the PP population will be the secondary efficacy analysis population.

Safety Population

The Safety population will include all patients who took at least one dose of study drug in the extension study.

ITT Population

The ITT population will include all enrolled patients who received at least one dose of study drug and have a baseline and at least one post-baseline efficacy assessment in the extension study.

PP Population

The PP population will include all enrolled patients who complete the extension study and have an efficacy assessment at the end of the study, have no major protocol violations, and have no change in DBS and baclofen pump settings or medications that could have an impact on dystonia. Prior to database lock, protocol deviations and medications that could have an impact on dystonia will be reviewed for their seriousness, and patients with major deviations will be excluded from the PP population.

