4.4 Safety Analyses

The safety endpoints include:

- Adverse events (AEs): Frequency, severity, time to onset, duration, and relatedness to study product
- Serious adverse events (SAEs): Frequency, severity, time to onset, duration, and relatedness to study product

-
- Number of discontinuations due to AEs
 - Hematology assessments
 - Blood chemistry assessments
 - ECG assessments

All safety data collected will be presented in listings and summary tables or graphs to give an overview of the safety findings. All safety endpoints will be analyzed based on the safety population. For patients continuing on deferiprone in the extension study, this time period will be from the start of TIRCON2012V1 to the completion of TIRCON2012V1-EXT; for those who received placebo in the initial study and are switching to deferiprone in the extension study, it will be from the start to the completion of the extension study.

For those patients who do not follow the scheduled time window exactly for each visit or withdraw from the study early, the following time window will be employed to classify the safety data into each scheduled visit according to the time elapsed from the first medication date (date of exposure) to the assessment date:

Month 1.5 visit: 0.75 to <2.25 months

Month 3 visit: 2.25 to <4.5 months

Month 6 visit: 4.5 to <9 months

Month 12 visit: 9 to <15 months

Month 18 visit: 15 to <21 months

Month 24 visit: 21 to <27 months

Month 30 visit: 27 to <33 months

Month 36 visit: 33 to <39 months

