4.4.1 Adverse Events

A summary table of adverse events will include the following information:

- number of patients exposed to study treatment,
- number of patients experiencing at least one AE,
- number of patients experiencing at least one severe AE,

- number of patients experiencing at least one serious AE,
- number of patients experiencing at least one drug-related AE,
- number of deaths,
- total number of patients withdrawn,
- number of withdrawals due to AEs.

All adverse experiences will be coded using MedDRA (Medical Dictionary for Regulatory Activities) and will be summarized by MedDRA System Organ Class (SOC) and Preferred Term. Adverse events will be defined as: 1) AEs that occurred or worsened (increased in intensity and/or frequency) on or after the first dose of study medication, 2) AEs with a missing start date or a stop date on or after the first dose of study medication, 3) AEs with both a missing start and stop date. Events that occur within 14 days after treatment discontinuation will also be considered AEs. Serious adverse events that occur within 30 days after treatment discontinuation will be included in the database.

Adverse events will be summarized using the total number of AEs, the total number and percent of patients who experience an AE, and the number and percent of patients who experienced an AE within each SOC (and preferred term within an SOC). The rate of each AE (per 100 patient years) will also be calculated. AEs will also be presented by intensity (mild, moderate, severe), by seriousness (serious, non-serious), and by relationship to study medication (at least possibly related, not related). The number and percentage of patients who are withdrawn from the study due to AEs will be calculated, and the AEs involved will be summarized in a frequency table. Time to onset and duration of all AEs with an incidence of >5%, and of any AEs of special interest (e.g., worsening of dystonia), will be summarized with descriptive statistics.

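### Pooled AE rates per 100 patient-years count initial-study time in which rolled-over deferiprone patients could not have had a participation-ending event; extension-only rates by initial arm are needed

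*SAP*

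**What the plan says.** **Who is in the set.** SAP 3.3: "The Safety population will include all patients who took at least one dose of study drug in the extension study". Protocol 4.2 makes "Completed study TIRCON2012V1" an inclusion criterion. Protocol 4.3 excludes anyone who "Withdrew from the study TIRCON2012V1 for reasons of safety". Protocol 4.5.2 adds: "The only individuals eligible for enrolment are those who completed treatment in study TIRCON2012V1".

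**Which period counts.** SAP 4.4: "For patients continuing on deferiprone in the extension study, this time period will be from the start of TIRCON2012V1 to the completion of TIRCON2012V1-EXT". For patients switched from placebo it is the extension only. SAP 3.5 matches this: day 1 for durations is the first exposure in the initial study for patients who were on deferiprone there, and the first exposure in the extension for the others.

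**What is reported.** SAP 4.4.1: "The rate of each AE (per 100 patient years) will also be calculated". The shells for Tables 14.3.1.2 to 14.3.1.8 show rates for a single pooled DFP group, each with a subject-years figure that is not split by period or initial arm. No AE or SAE shell shows the extension alone or separates the Placebo-DFP and DFP-DFP groups. Deaths, withdrawals and AE withdrawals appear in Table 14.3.1.1 as n (%).

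**Competing definitions.** Protocol 9.4.1.4 opens broadly, with "All safety data reported and collected during deferiprone therapy for all patients will be presented in listings and summary tables", and then limits this to continuing and switching patients, in line with SAP 3.3. The footnote to Table 14.2.1.2 instead defines the DFP group as anyone who ever took the drug in either study, and extends that to every table with this group. The protocol Synopsis and Protocol 9.3.3 are also looser than SAP 3.3.

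**Disposition and exposure.** SAP 4.1 and Tables 14.1.2, 14.1.3 and 14.1.5 use the ITT population, which requires a post-baseline efficacy assessment in the extension. The duration categories in Table 14.1.3 stop at 18 months.

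**The concern.** A DFP-DFP patient is in the safety set only because he or she got through the initial study. That patient's first 18 months on drug were therefore selected to contain no death and no withdrawal. The time still goes into the rate denominator, while an event that ended participation during it cannot go into the numerator, because the patient who had it is not in the set. This is immortal time, and it lowers the rate of exactly those AE terms that make patients leave.

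Long-term safety and tolerability is the primary objective. Protocol 1.3 names agranulocytosis as the most serious event with this drug. In the extension, "Occurrence of moderate neutropenia or severe neutropenia/agranulocytosis" requires withdrawal (Protocol 4.5), so the affected terms may include the ones readers look at first. With one pooled column and no extension-only table, the AE tables give no way to separate the two periods.

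**Working it through.** The documents state no patient-year or rate figure to reproduce, and SAP 3.2 says there was no formal sample-size calculation. The one available check is 44 + 24 = 68, which agrees with the stated enrolment.

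**Inputs.** 44 enrolled from the deferiprone arm and 24 from placebo (SAP 3.2). Each study lasts 18 months, or 1.5 years (SAP 3.1). Safety periods are from SAP 4.4. Actual follow-up is not given, so planned follow-up is used first and then varied.

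**Step 1: person-time at plan.**
- Initial-study time of DFP-DFP patients: 44 × 1.5 = 66
- Extension time of all patients: 68 × 1.5 = 102
- Counted in the pooled rate: 66 + 102 = 168
- Share in which a participation-ending event cannot appear: 66/168 = 39%

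**Step 2: a term that always ends participation.** All its events fall in the extension, so the numerator is the same for both rates and only the denominator differs.
- Planned rate per event: 100/168 = 0.60 per 100 patient-years
- Extension-only rate per event: 100/102 = 0.98
- Factor: 168/102 = 1.65

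**Step 3: dropout from the extension.** If extension person-time is 80% of plan (assumption), it is 0.8 × 102 = 81.6. The total is 81.6 + 66 = 147.6, and the factor is 147.6/81.6 = 1.81.

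**Step 4: a term that ends participation only sometimes.** Let a share f of its events end participation, with the same underlying rate L in both periods (assumption). The expected planned rate is L × (102 + 66(1 − f))/168 and the extension-only rate is L, so the factor is 168/(168 − 66f). At 80% extension time it is 147.6/(147.6 − 66f).

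| f | Full follow-up | 80% extension time |
|---|---|---|
| 1 | 1.65 | 1.81 |
| 0.5 | 1.24 | 1.29 |
| 0.25 | 1.11 | 1.13 |
| 0 | 1.00 | 1.00 |

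**Step 5: a rate that changes with time on drug.** Here the comparison is with the rate that unselected patients would show over the same 168 patient-years. Let h1 apply in months 0–18 on drug and h2 in months 18–36. Months 0–18 account for 66 + 24 × 1.5 = 66 + 36 = 102 patient-years, of which only the 36 can show the event. Months 18–36 account for 66. The factor is (102h1 + 66h2)/(36h1 + 66h2): 1.65 at h2 = h1, 1.96 at h2 = 0.5h1, and 1.39 at h2 = 2h1. The documents do not say which pattern applies.

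**Step 6: disposition.** An enrolled and dosed patient who leaves before any post-baseline efficacy assessment is in the Safety population but not in the ITT population. That patient is missing from Tables 14.1.2 and 14.1.5, although disposition is meant to describe everyone enrolled.

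**The case against.** - **The denominator is never defined in words.** This stands. That initial-study time is included is inferred from SAP 3.5, SAP 4.4 and the shells. If the footnote to Table 14.2.1.2 governed the AE tables, early stoppers would be counted and this dilution would not arise. But the AE tables are titled as safety-population tables, so SAP 3.3 is the better guide. The conflict itself needs resolving.
- **The initial study's withdrawal rules are not in the documents.** This also stands. A reader might infer that the planned agranulocytosis rate is certainly low by the full factor. The documents do not support that: the mandatory-withdrawal rule shown is the extension's. Mild neutropenia allows treatment to restart (Protocol 7.2.1.8), so a broad neutropenia term is only partly affected.
- **The rates are descriptive.** They are an SAP addition that is not among the protocol's endpoints, and counts stand beside them. SAEs, AE withdrawals and deaths are listed and narrated. With a single event, exact Poisson 95% limits are about 0.02 to 3.3 (168 patient-years) and 0.02 to 5.5 (102 patient-years) per 100 patient-years, so 0.60 and 0.98 cannot be told apart statistically. This limits the consequence but does not remove a systematic shift.
- **Cumulative reporting is a design choice, and selection is inherent to an extension.** This is partly right. Of 89 randomised, 89 − 76 = 13 stopped early and 76 − 68 = 8 completed without enrolling; their arms are not stated. No extension can recover them, and extension-only rates still describe DFP-DFP patients who had already completed 18 months. But putting those completers' earlier time into a pooled rate is a choice.
- **Early leavers are partly covered.** Table 14.3.1.1 gives total and AE withdrawals on the Safety population, and the early termination visit includes the BAD and PGI-I. The disposition gap is therefore probably small.

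**Conclusion.** The concern holds for AE terms that end participation. On the natural reading of the SAP, about 39% of the planned rate denominator cannot contain such an event. For a term that always ends participation, the extension-only rate is about 1.65 times the planned rate. The ratio of the two reported rates rests on full planned follow-up. Reading it as the understatement of the underlying rate also needs a constant rate.

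Three stronger readings are not supported:

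- A reader might take 1.65 as the most the dilution can be. It is not: dropout from the extension raises it, to 1.81 at 80% of planned extension time.
- A reader might conclude that all AE rates are diluted. Terms that do not end participation are unaffected by this mechanism, and terms that do so a quarter of the time shift by a factor of only about 1.11.
- A reader might conclude that deaths and AE withdrawals are understated. They are reported as n (%), and Table 14.1.5 splits reasons for not completing by group, so these outputs are not diluted. They are valid for the extension, but they are not a cumulative deferiprone figure.

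The ITT basis for disposition is a separate and smaller defect. Overall this is a cheap improvement to the primary safety reporting and worth making. It does not show that the safety data are misreported.

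**What to change.** 1. Add AE and SAE tables for the extension period only, using extension person-time and split into Placebo-DFP and DFP-DFP. The split also separates months 0–18 on drug from months 18–36, so a constant rate need not be assumed.
2. State the rate denominator in SAP 4.4.1. Label the cumulative tables as covering rolled-over patients only. Reconcile the footnote to Table 14.2.1.2, the Synopsis and Protocol 9.3.3 with SAP 3.3.
3. Base disposition and reasons for not completing on all enrolled patients, and exposure on the Safety population. State the period that Table 14.1.3 covers, and extend its categories if initial-study time is included.

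The cost is some SAP wording and a few more tables from data already held. Some rates may look less favourable.

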3.4 Interim Analysis

No interim analysis is planned.

3.5 Missing Data Handling and Derivation Rules

For safety data analysis, no imputation will be performed on the missing data and analysis will be based on observed cases.

For efficacy endpoints, the continuous variables will be summarized and analyzed as recorded on the case report forms (CRFs). If statistically significant imbalances are detected in the incidence of changes in DBS settings and outcome impacting medication use as well as the frequency of PRN drug or rescue medication between the initial study and the extension study, a Mixed-Effect Model Repeated Measure (MMRM) model will be used as the analysis method to compare the change in score from baseline between the initial study and the extension study for patients who received placebo in initial study (TIRCON2012V1) and the analysis will be based on observed cases. If no significant imbalance was detected, the paired t-test will be used as the analysis method and the last observed data will be used.

For the efficacy analysis on all patients who received DFP during the initial and the extension study, the last observation will be used to calculate the change from baseline for patients terminated early. As a sensitivity analysis, for early termination due to worsening of disease conditions or inadequate efficacy of the drug, as indicated in the CRF, the “worst score” method will be used for data imputation. That is, for continuous variables such as BAD total score at a particular time point, the worst score of all patients will be used to impute the missing data at that time point. For categorical variable such as responder, the worst category (treatment failure) will be assigned. For missing data due to missed visit, the last observation will be used to fill the void.

For BAD total score, if one or several component scores cannot be measured, then the same component score from the last visit will be carried forward and if it is also missing, the score from the next visit will be carried backward to fill the missing component score(s) before the total score is calculated.

Date of exposure will be defined as day 1 for all duration calculations. For example, age at entry will be calculated as the integer value of the expression: (date of exposure – date of birth) / 365.25. For patients on DFP in the initial study, the date of exposure during the initial study (TIRCON2012V1) will be used while for those switched from placebo to DFP in the extension study (TIRCON2012V1-EXT), the date of exposure during the extension study will be used.

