5 STUDY PROCEDURES

The procedures and assessments to be conducted at each study visit are summarized in [Table 5.1](#) and are detailed in the section that follows.

Table 5.1 Table of study procedures

Procedure	Visit 1 ¹	Weekly Blood Draws	Telephone Contact	Visit 2	Visit 3	Visit 4 or Early Termination
Week:	0	1 to 78	1 and 2	26	52	78
Informed consent/assent	X					
Confirmation of eligibility	X					
Review of medical history	X					X
Serum pregnancy testing ²	X			X	X	X
Physical examination	X			X	X	X
Vital signs (including weight and height) ³	X			X	X	X
12-lead ECG	X					X
Contraceptive counseling	X			X	X	X
Hematology	X	X		X	X	X
Blood chemistry	X			X	X	X
Urinalysis	X			X	X	X
BAD	X			X	X	X
PGI-I				X	X	X

Procedure	Visit 1 ¹	Weekly Blood Draws	Telephone Contact	Visit 2	Visit 3	Visit 4 or Early Termination
Week:	0	1 to 78	1 and 2	26	52	78
Dose calculation/verify and adjust dose level	X			X	X	
Dispense study medication	X			X	X	
Remind patient to adjust dosage ⁴			X			
Collect used and unused study medication				X	X	X
Prior and concomitant medications	Throughout the study					
Adverse events and serious adverse events	Throughout the study					

¹ Visit 1 is the final visit (Month 18) of study TIRCON2012V1. It serves as the screening visit for TIRCON2012V1-EXT for all patients, and as the baseline for those patients who received placebo in TIRCON2012V1 and will now be receiving deferiprone for the first time. (For patients who received deferiprone in TIRCON2012V1, the measures obtained at the baseline visit of the TIRCON2012V1 study will be used as the baseline measures for TIRCON2012V1-EXT as well.)

² Sexually active females of childbearing potential only (if applicable; in cases where the investigator determines there is no reasonable risk of pregnancy because of significant incapacity, pregnancy testing will not be performed).

³ Height will be measured only at Visits 1 and 4

⁴ All patients, including those who were on deferiprone initially, will receive 5 mg/kg deferiprone b.i.d. for the first week. If the medication is tolerated and there are no signs of toxicity, the dose will be increased at Week 1 to 10 mg/kg b.i.d., and will be increased again at Week 2 to 15 mg/kg b.i.d. for the remainder of the study. Patients will receive a telephone call at these times to remind them to implement the increase in dosage, provided there are no safety concerns in doing so.

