4.3.1 Efficacy Endpoints

All patients:

For the efficacy measures of BAD (total score and by body region) and PGI-I, the value at each of the measurement time points defined in section 4 will be determined and summarized using descriptive statistics for all patients on DFP treatment. Similar data will also be presented by the treatment group received in initial study.

A paired t-test will be used to assess the statistical significance of the changes in these efficacy outcomes from baseline to the end of study (Visit 4, month 18 or 36 as defined in section 4).

For the BAD total score and for PGI-I, the proportions of patients determined to be responders at the end of study (Visit 4) will be calculated and presented along with 95% confidence intervals.

The mean trajectory of BAD (total score and by body region) and PGI-I by time will be plotted. The longitudinal trend for BAD total score and by body region will be explored by the MMRM model with time modelled as a continuous variable as defined in section 4 for all time points where patients were on DFP.

Patients who received placebo in initial study:

For the efficacy measures of BAD (total score and by body region) and PGI-I, the value at each of the measurement time points defined in section 4 will be determined and summarized using descriptive statistics for each study period.

A paired t-test will be used to compare the change in BAD (total score and by body region) between the start and completion of the initial study to that between the start and completion of the extension study. The same test will be repeated for the PGI-I data.

The incidence of changes in DBS settings and outcome impacting medication use as well as the frequency of PRN drug or rescue medication use will be tabulated and compared between the initial study and the extension study. If statistically significant imbalances are detected, they will be adjusted accordingly for the comparison of changes in BAD and PGI-I between the initial study and the extension study by using the MMRM model as defined in section 4.

For the BAD total score and for PGI-I, McNemar's test will be used to compare the proportion of responders in the initial study with the proportion of responders in the extension study.

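### For the former-placebo patients, SAP 3.5 ties the missing-data rule to imbalance tests and leaves it unsettled once one is significant; its last-observation rule shortens only the deferiprone period, and the sample MMRM cannot be fitted as coded

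*SAP*

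**What the plan says.** SAP 3.5 sets an either/or for patients who took placebo in the initial study. If the tests on DBS settings, outcome-impacting medication and PRN or rescue frequency show a significant imbalance between the two studies, the comparison is an MMRM on observed cases. If not: "If no significant imbalance was detected, the paired t-test will be used as the analysis method and the last observed data will be used".

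SAP 4.3.1 has no such condition: "A paired t-test will be used to compare the change in BAD (total score and by body region) between the start and completion" of each study. The MMRM then enters as an adjustment: "If statistically significant imbalances are detected, they will be adjusted accordingly for the comparison of changes in BAD and PGI-I". SAP 4 frames it the same way. The table shells include paired t-test tables (14.2.2.2, 14.2.2.6) and an MMRM table (14.2.2.9), none marked as conditional.

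On who is analysed, Protocol 4.2 requires "Completed study TIRCON2012V1", and Protocol 4.5.2 adds that "The only individuals eligible for enrolment are those who completed treatment in study TIRCON2012V1". Protocol Table 5.1, footnote 1, states that "Visit 1 is the final visit (Month 18) of study TIRCON2012V1", which is also the baseline for former-placebo patients. The ITT population (SAP 3.3) must "have a baseline and at least one post-baseline efficacy assessment in the extension study"; it need not have Visit 4.

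The sample MMRM code in SAP 4 uses `VISIT` as the repeated effect within `USUBJID`, with AR(1) covariance, and takes the baseline value as covariate `BASE`.

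**The concern.** How to treat patients who leave early has nothing to do with whether DBS or medication changes differ between periods, yet one set of tests decides both. If an imbalance is found, SAP 3.5 moves to the MMRM, while SAP 4.3.1 and the shells still call for a paired t-test. A reader could not tell what data stand behind that p-value.

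The last-observation rule also acts on one side only. A full 18-month placebo change is set against a deferiprone change that may stop at 6 or 12 months. The protocol describes PKAN dystonia as progressive, so a shorter interval may show less worsening with no drug effect at all. The McNemar responder test lies outside the imbalance gate but has the same exposure if last values are used.

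The listed checks cover this only in part. The per-protocol set contains completers, but it must also "have no change in DBS and baclofen pump settings or medications that could have an impact on dystonia", so it does not isolate dropout. The imputation tables (14.2.1.15s, 14.2.1.16s) belong to the all-patients analysis.

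**Working it through.** The plan states no sample size, power or bias figure here, so there is nothing to reproduce. SAP 3.2 gives 44 + 24 = 68 enrolled, which adds up.

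**Inputs from the documents.** 24 former-placebo patients, and 76 of 89 completing the initial study (SAP 3.2); two-sided 0.05 (SAP 3.6); BAD 0 to 32, higher is worse (Protocol 7.1.1).

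**Assumptions.** The documents give no progression rate, SD or extension dropout. Assumed: dropout d = 13/89 = 14.6%, borrowed from the initial study (about 3.5 of 24 patients); worsening r of 2 or 4 points per 18 months, at the same rate in both periods; slope SD 2; residual SD 1.5; no drug effect.

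**Last-observation bias, dropout unrelated to outcome.** With last value at month t:

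bias = −d × r × (1 − t/18)

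- Last seen at Month 6 or 12 (mean 9): −0.146 × 2 × 0.5 = −0.15; with r = 4, −0.29.
- Early-termination value at a uniform time from Month 3 to 18 (mean 10.5): −0.146 × 2 × 0.417 = −0.12; with r = 4, −0.24.

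Simulated paired t-test, n = 24:

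| Setting | Bias, r = 2 / r = 4 | Two-sided error |
|---|---|---|
| Last seen Month 6 or 12 | −0.14 / −0.29 | 5.2% / 6.5% |
| Early-termination value, Month 3 to 18 | −0.12 / −0.24 | 5.3% / 6.0% |
| Dropout partly driven by observed worsening | −0.06 / about −0.20 | 5.2% / 5.8% |
| Worst observed changes leave | 0.00 to +0.03 / −0.10 to −0.12 | 5.1% / 5.3% |

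With unrelated dropout, no mean change gives a bias of 0.00, and improvement of 2 points gives +0.15, against deferiprone.

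**Scale.** The difference of the two changes is e(36) − 2e(18) + e(0), with variance 6 × 1.5² = 13.5. The 95% CI half-width is 2.069 × √13.5/√24 = 1.55 points. The bias with unrelated dropout is 0.12/1.55 = 8% to 0.29/1.55 = 19% of that.

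**Other endpoints, same assumptions.** BAD responder rates, placebo against deferiprone: 24.6% vs 26.0% (r = 2) and 8.5% vs 10.3% (r = 4). PGI-I, if its mean drifts 0.5 or 1.0 category by Month 18: −0.146 × 0.5 × drift = −0.04 or −0.07.

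**Same-month comparison.** Each early stopper is compared with the same patient's placebo value at that month. With unrelated dropout the bias is within 0.005 and two-sided error is 4.9 to 5.1%. Matching by the SAP 4 visit windows gives −0.006 / −0.010 and 5.0% / 4.8%. With partly outcome-driven dropout the bias is about 0.01; if the worst observed changes leave, it is about +0.04, against deferiprone.

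**The gate.** Three independent tests at 0.05 would switch the rule in 1 − 0.95³ = 14.3% of trials with no true imbalance. This is an upper guide, since exact McNemar is conservative at n = 24. With true discordant rates of 30% and 10%, McNemar detects the imbalance in 23% (exact) to 32% (asymptotic) of trials.

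**MMRM as coded.** Each patient has three visits in each of two periods, with the same `VISIT` labels. The AR(1) structure then gives two records with the same label a correlation of 1. The 6 × 6 matrix repeats one 3 × 3 AR(1) block four times: rank 3, determinant 0.

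**MMRM with only that repaired.** `BASE` is each period's own baseline, and the extension baseline already contains the placebo-period change, so its mean is higher by r. A negative `BASE` slope b shifts the period contrast by −b × r. Simulated without dropout or drug effect: +0.35 / +0.70 points at an assumed baseline SD of 4 (0.35/2 = 0.70/4 = 0.175 per point), and +0.12 / +0.25 at SD 7 (about 0.06 per point). Positive is against deferiprone. With `BASE` dropped, the bias is within 0.01 and error is 2.5 to 3.8% per side against a nominal 2.5%.

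**The case against.** The strongest reply is that the sections describe one sequence: paired t-test by default, MMRM if an imbalance appears. Protocol 9.4.1.3 contains the same gate, and SAP 4.3.1 states no competing missing-data rule. This stands in part. A reader might infer two rival missing-data rules, and the text does not support that. The sections differ on whether the t-test is conditional, and what is missing is the data rule for a t-test reported after an imbalance.

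A second reply is that the direction is not fixed. SAP Table 14.1.5 lists worsening or lack of efficacy as a reason for leaving, and early-termination visits record BAD and PGI-I. If worsening drives dropout, the carried value is already a bad one and the bias shrinks or slightly reverses. This stands. A reader might infer that the rule always flatters deferiprone; that needs continued worsening and dropout largely unrelated to it.

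Third, the one-sidedness is strict only for BAD total score. A missing Visit 1 PGI-I form need not remove a patient from ITT, so an earlier placebo-period rating could be carried forward, and the component carry-forward rule in SAP 3.5 can touch either period. This also stands.

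Fourth, the code is labelled a sample, and SAP 5 and 7 allow tables to be added or changed. That makes repair easy, but the model still cannot be run as written. A reader might infer that the planned MMRM leans against deferiprone. That bias belongs to a half-corrected model and varies with the assumed baseline SD; as coded, there is no valid fit to lean either way.

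**Conclusion.** The point holds in limited form and should be corrected. The unsettled rule and the singular covariance follow from the text and code and need no assumptions.

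The size of the last-observation bias does rest on assumptions. Under those used here it is modest, and at two-sided 0.05 the excess error is at most about 1.5 percentage points. It would be larger with heavier dropout: at 30% and 4 points of worsening, −0.60 points and 10.8% two-sided.

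The comparison is secondary and open-label with a fixed treatment order. Restricting entry to placebo completers may itself act in the other direction, by an unknown amount. None of this bears on the primary safety objective.

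**What to change.** 1. In SAP 3.5, set one missing-data rule for the paired t-test whatever the imbalance tests show, and align SAP 4.3.1. Keep the protocol's paired t-test as the lead. For each early-stopping patient, compare the deferiprone BAD change, PGI-I and responder status with that patient's own placebo result at the same month. Initial-study visits include Months 6 and 12 (Protocol 1.2), and the 14.2.2 shells already show placebo values there. State how an assessment before Month 3, which falls in no efficacy window, is handled. Report the last-observation version as a sensitivity analysis.
2. Keep the imbalance tests as description (Table 14.2.2.8). Change the MMRM's repeated effect to period-by-visit within patient, and drop `BASE` or use the single initial-study baseline for both periods; treat the baseline BAD score in the PGI-I model likewise. Report the MMRM as supporting only, whatever the tests show. Its covariates are measured after treatment starts, and its error rate is approximate because the Month 18 placebo value enters both periods' changes.
3. Document any departure from Protocol 9.4.1.3 in the study report, as Protocol 9.4 requires. This includes any departure from the initial study's model, which the documents do not show.

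The cost is wording in SAP 3.5, 4 and 4.3.1, two corrected code statements, one added table and some programming. The downside is that for dropouts the contrast falls earlier than 18 months, so a slow drug effect may be diluted.
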